Other effect measures are calculated with t-test for two independent groups or a corresponding non-parametric test, depending on the distribution of the material. A significance level of 0.05 will be used. Primarily, data will be analyzed according to the "intention-to-treat" principle, although secondarily an "on treatment" analysis will be carried out, where the degree of compliance is corrected.

The intention-to-treat population consists of all participants who have been randomized to the study and who have received at least one dose of the study medication. In the event of missing data in the Intention-to-treat analysis, "last value carried forward" will be used. In the final protocol, there will be an account of unused or omission of inauthentic data, as well as an account of reasons for any deviations from the originally planned statistical analyses.

It is planned to carry out interim analyzes when the sub-cohort of 100 subjects (which includes mainly from Aarhus University Hospital and Regional Hospital Silkeborg) has completed the entire study program. This is to ensure that this population can be included in a data analysis which will form the basis of a PhD thesis

Study population

260 patients, men and women, with newly diagnosed GS where anti-thyroid treatment is planned. Potential study participants are recruited from hospitals in Central Denmark Region in connection with patients' attendance at the outpatient clinic.

Inclusion criteria

- Newly diagnosed Graves' disease verified by TSH below the reference range and thyroxin and/or triiodothyronine (T3 and/or T4) above the upper reference range.
- Age 18 years or older
- Elevated plasma level of thyroid stimulating immunoglobulin (TRAb)

- Planned or started (< 3 months) medical anti-thyroid treatment
- Speaks and reads Danish.
- Written consent after oral and written information

Exclusion criteria

- Daily intake of vitamin D supplements of more than 10 micrograms, which the participant wishes to continue.
- A previously diagnose of hyperthyroidism
- Planned treatment with radioactive iodine or thyroidectomy
- Chronic granulomatous disease
- Significant hypercalcemia (ionized plasma calcium $> 1.40 \text{ mmol/l}$)
- Reduced kidney function (eGFR $< 45 \text{ ml/min}$)
- Regular intake of medication with known immuno-modulating effects, including systemic glucocorticoids ($>5\text{mg/day}$ for 3 months), imurel, methotrexate, TNF α -inhibiting agents.
- Active malignant disease

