Vitamin D and bone turnover, muscle function tests and cardiovascular indices

Bone turnover.

Based on the experience from other intervention studies with vitamin D, it is considered reasonable to expect that treatment with vitamin D will cause at least a 2% difference between the intervention and placebo groups. With measurements carried out on the lumbar spine (L1-L4), where it can be assumed that the mean BMD is 0.920 g/cm^2 (SD 0.03 g/cm^2), the required number of participants can be calculated - as it is desired to be able to demonstrate a 2% difference between the 2 groups - based on the following formula ($\alpha= 0.05$; $C2\alpha = 1.96$. $\beta= 0.20$; $C\beta = 0.84$):

$$N = (C2\alpha + C\beta)^2 \times (2 \times \text{SD} / (\text{Mean} \times 0.02))^2 = 72 \text{ participants.}$$

Since 100% compliance cannot be expected and since some of the participants may drop out during the study period, it is reasonable to increase the number of participants. Thus, a total of 100 participants will be included, randomized equally to either treatment with placebo or vitamin D supplementation.

There are no applicable data for strength calculation for the effect of vitamin D supplementation on muscle function tests and cardiovascular indices in patients with Graves' disease.

Pulse wave velocity. A recent meta-analysis has shown that an increase in pulse wave velocity of 1 m/s leads to a 15% increase in total and cardiovascular mortality⁴¹. With 50 patients in each group, and given that the standard deviation in each group is 1.5 m/s, it will be possible to detect a difference of 1 m/s with a power of 92% ($\alpha=0.05$).

Intervention and randomization

Vitamin D supplements

In the study, vitamin D tablets of 70 µg and a corresponding placebo are used, which are supplied free of charge by Orkla Health.

The project medication is packaged and labeled according to the Danish Medicines Agency's regulations by the Hospital Pharmacy at Aarhus University Hospital.

Vitamin D supplements and placebo tablets will be packed in quantities corresponding to 3-9 months' consumption and handed out to the participants upon attendance or forwarded by agreement at the regular contacts. (figure 1)

Procedures for randomization

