Furthermore, adiponectin, leptin, insulin. Markers of the renin-angiotensin-aldosterone system. Organ-specific antibodies, including TPO antibody, transglutaminase antibody IgA, total IgA, deamidated gliadin peptide antibody IgG, and markers of immune system activity, including high resolution CRP and immunoglobulins.

Furthermore, selected inflammatory and pro-inflammatory markers as well as adipokines. DNA is taken from leukocytes for genetic studies, see below.

Flow cytometry will be performed on fresh blood at the Department of Clinical Immunology, Aarhus University hospital, where lymphocyte subpopulations and cell differentiation will be examined. In cell culture studies, dendritic cells and their co-stimulatory factors will be examined. In addition, measurement of soluble HLA-G as well as functional studies of the regulatory T cells' suppressor function will be performed.

Surveys

A sub-cohort of 100 test subjects will complete the study program below, see figure 2. Separate information material has been prepared for this, see appendix 5.

Baseline examinations will be carried out within 14 days of referral.

Examinations at three and nine months will be carried out with a precision of +/- four weeks.

The examinations (including biopsies) will be repeated in connection with the end-of-study blood test after a renewed information interview and informed consent. Only participants who have previously participated in this research program and who continue to participate in the DAGMAR study will be able to participate. Pregnancy is an exclusion criterion. The background for the repeated examinations is that at the nine month investigations, especially the muscle strength testing, there are signs of continued improvement. Long-term clinical studies in Graves' disease on these aspects are currently limited or non-existent. It is therefore unclear when final restitution will be achieved, which these studies will be able to help shed light on.

Osteodensitometry

Bone scans will be performed as a "Dual-Energy X-ray absorptiometry" (DEXA) scan with a Hologic QDR Discovery scanner. BMC and BMD will be measured in the lumbar spine (L1-L4), the hip region (femoral neck, trochanter, Ward's triangle and intertrochanteric region), the forearm (proximal, middle 1/3 and ultra-distal) and the whole body. Furthermore, body composition will be determined.

HRpQCT scan

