Inclusion criteria

- Between 18 and 80 years old
- Euthyroidism
- Speaks and reads Danish
- Written consent after oral and written information

Exclusion criteria

- Current or previous metabolic disease
- Significant other disease, including renal impairment (eGFR <60 ml/min, hypercalcemia, treatment with the glucocorticoid system.
- Known neuromuscular disorders
- Pregnancy
- Alcohol abuse resulting in the need for treatment or hospitalization
- Abuse of euphoric substances

Statistics/strength calculation

In our research group, in a previous study on healthy adults, we have found that the mean value for maximum knee flexion at 90 degrees is 463N with a standard deviation of 170 N. To detect a difference between groups of 20% with a power of 0, 80 given a significance level of 0.05, 53 participants are required in each group.

During thyrotoxicosis, the loss of bone mass has been estimated at 9% per remodeling cycle. Assuming that the average lumbar bone mass density is 0.92 g/cm² (SD 0.11 g/cm²), with the

stated population size we will be able to demonstrate a difference between groups of 10% at baseline with a power of 0.97 ($\alpha=0.05$).

A recent meta-analysis found that the risk of all-cause mortality and cardiovascular death increased by 15% for an increase in pulse wave velocity (PWV) of 1 m/s. Given a standard deviation of 1.5 m/s in each group, the study size will be able to demonstrate a difference between groups at a baseline of 1 m/s with a power of 0.94 ($\alpha=0.05$).

Data collection

Survey program

The participants complete an examination program similar to the baseline examinations for the intensively examined cohort in the randomized clinical trial:

Baseline

Health information

Blood tests

Questionnaire about i.a. quality of life

DXA scan

HRpQCT scan

Arterial stiffness and blood pressure measurement

Muscle and balance function examination

Follow-up, carried out with a precision of +/-4 weeks

Blood tests

questionnaire

Muscle and balance function

Arterial stiffness and blood pressure measurement

Health information and questionnaire

Participants answer the same baseline, ThyPRO and follow-up questionnaire as approved for the main study.

Based on the interview and questionnaire, the following will be registered in the CRF:

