The study was created on the initiative of doctors from the Department of Medical Endocrinology, Aarhus University Hospital. No one from the project group has financial interests in the study.

Expenses for the investigation will be financed by the departments involved, as fund support is also applied for.

No financial remuneration is provided to the test subjects, but possibly a transport allowance.

Study medication in the form of vitamin D and placebo is provided free of charge by the food manufacturer and dietary supplement manufacturer Orkla Health.

Figure 1. Flow-chart showing the course of treatment and investigations in the individual participants (n=260) randomized to treatment with vitamin D or similar placebo.

*In a sub-cohort of 100 participants additional measurement will be performed in terms of: blood pressure, pulse wave velocity (arterial stiffness), muscle- and balance-measurements, bone mineral density (BMD) and body composition (by DXA-scans), 3D bone microstructure (by HR pQCT- scans), and immunological analysis. From this sub-cohort 30 participants will undertake muscle and fat biopsy at baseline, 3 and 9 months.

Statistical analysis plan, final

Analyses of treatment effects will be based on the intention-to-treat principle. The first analysis will compare baseline characteristics by randomized treatment assignment to ensure that balance was achieved by the randomization. Characteristics to be examined include known risk factors for treatment failure including age, sex, smoking habits, severity of thyrotoxicosis, former use of vitamin D and baseline vitamin D status.

Differences between groups will be evaluated using a Chi Square test for categorical variables and a two-sample *t* test or Wilcoxon ranksum test, as appropriate, for continuous variables. For the primary outcome, the risk of treatment failure will be calculated as risk ratio (RR) with 95% confidence interval (CI).

With the intention-to-treat (ITT) approach, all subject who had been randomized and had received at least one dose of study medication will be included in the analysis. If study outcome is unknown, e.g. study withdrawal or exclusion, participants will be included in the ITT assuming either a *worst-case scenario* (all had treatment failure) or a *best-case scenario* (all experienced a treatment success)

In per-protocol analyses, only participants in whom outcomes can be assessed will be included.

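### The bone-density sample size formula gives 84 participants, not the 72 stated, and its SD of 0.03 g/cm² is neither labelled nor reconciled with the 0.11 g/cm² used elsewhere for lumbar BMD

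*Combined protocol and SAP*

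**What the plan says.** **Sub-cohort calculation.** The protocol's Population size section, under bone turnover, plans for a 2% difference in lumbar spine (L1-L4) BMD between vitamin D and placebo, "where it can be assumed that the mean BMD is 0.920 g/cm^2 (SD 0.03 g/cm^2), the required number of participants can be calculated". It prints the constants 1.96 and 0.84, the formula, and a result of 72. It then argues that full compliance cannot be expected and that "since some of the participants may drop out during the study period, it is reasonable to increase the number of participants", and sets the sub-cohort at 100, randomised equally. No drop-out rate is given.

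**Control-cohort calculation.** The Statistics/strength calculation for controlled cohort study ii) uses the same lumbar mean with a different spread: "Assuming that the average lumbar bone mass density is 0.92 g/cm² (SD 0.11 g/cm²". From this it claims to be able to "demonstrate a difference between groups of 10% at baseline with a power of 0.97".

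**Measurement.** Under Surveys, the sub-cohort is examined at baseline and again later: "Examinations at three and nine months will be carried out with a precision of +/- four weeks". A repeat at the end of the study was added.

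**Analysis.** The original SAP states: "Other effect measures are calculated with t-test for two independent groups or a corresponding non-parametric test". The final SAP names a two-sample *t* "test or Wilcoxon ranksum test, as appropriate, for continuous variables". Neither says whether the variable tested is the follow-up level or the change from baseline, and neither mentions adjustment for baseline.

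**The concern.** Two things do not fit. First, the protocol prints every input to its formula, and putting them in does not return 72. Since 100 is presented as 72 plus a margin for losses, an error in 72 is an error in the margin.

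Second, the text attaches the SD of 0.03 to mean BMD, so it reads as the spread of BMD between people. The same protocol puts that spread at 0.11 around the same mean, almost four times larger. The two figures can coexist if 0.03 describes within-person change or the residual after baseline adjustment, but the protocol does not say so, and the SAPs do not name an analysis that would make it so. The required number goes with the square of the SD, so which quantity 0.03 describes decides whether 100 participants can show a 2% difference. Effects on bone are part of the trial's secondary hypotheses, and for the bone, muscle and cardiovascular outcomes this is the only calculation that derives a required number for the randomised sub-cohort. The pulse wave velocity figure starts from 50 per group.

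**Working it through.** **Inputs** (Population size, bone turnover): mean 0.920 g/cm², SD 0.03 g/cm², difference 2%, constants 1.96 (α = 0.05) and 0.84 (β = 0.20), equal allocation, 100 planned. From the control-cohort calculation: mean 0.92, SD 0.11 g/cm².

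**1. The plan's own figure.** The difference is 0.920 × 0.02 = 0.0184 g/cm². The printed formula is the total number for two equal arms:

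N = (1.96 + 0.84)² × (2 × SD / 0.0184)²

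- With SD 0.03: 7.84 × (0.06 / 0.0184)² = 83.4, so 84 in total (42 per arm). The stated 72 is not reproduced.
- Variants also miss: exact normal quantiles 83.5; one-sided α 66; power 75% 73.8; power 90% 111.7; difference rounded to 0.02, 70.6.
- Solving for the SD that gives 72: √72 / 2.8 × 0.0184 / 2 = 0.0279.
- The SD is printed to one significant figure. Across values that round to 0.03, SD 0.025 gives 58 and SD 0.035 gives 114.

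**2. Power at SD 0.03** (two-sample t-test, two-sided 0.05, difference 0.0184):

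| Total evaluable | Power |
|---|---|
| 72 | 73% |
| 84 | 79% |
| 86 | 80% |
| 100 | 86% |

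The margin within 100 is 100 − 72 = 28 as the plan implies, and 100 − 84 = 16 on the printed inputs (14 on the t-test number of 86).

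**3. What 0.03 would have to be.** Assume a between-person SD of 0.11 at both visits and baseline/follow-up correlation ρ.

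- SD of change = 0.11 × √(2(1 − ρ)). Setting this to 0.03 gives ρ = 1 − 0.03² / (2 × 0.11²) = 0.963.
- Residual SD in ANCOVA = 0.11 × √(1 − ρ²). Setting this to 0.03 gives ρ = √(1 − (0.03/0.11)²) = 0.962.

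Power for a 2% difference with 50 per arm:

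| ρ (assumed) | SD of change | Power | Residual SD | Power |
|---|---|---|---|---|
| 0.90 | 0.0492 | 46% | 0.0479 | 48% |
| 0.95 | 0.0348 | 75% | 0.0343 | 76% |
| 0.97 | 0.0269 | 92% | 0.0267 | 93% |

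**4. Unadjusted follow-up levels, SD 0.11.** The printed formula gives 7.84 × (0.22 / 0.0184)² = 1,121 participants. With 50 per arm, power for 2% is about 13%, and the difference detectable with 80% power is 0.062 g/cm², which is 0.062 / 0.92 = 6.8%.

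**The case against.** The best reply on the arithmetic is rounding. The mean is printed to three decimals and the SD to one significant figure. An SD of 0.0279 prints as 0.03 and gives 72, so 72 may have been computed correctly from a value the reader cannot see. This stands as a possible explanation, and it is why the conclusion is that 72 does not follow from the figures as printed, not that 84 must be the true number. It does not rescue the text: no section gives the finer value, and the same rounding interval reaches 114, above the 100 enrolled.

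Next, the design may not change. The 100 enrolled exceeds 84 and 86, and 80% power holds up to an SD of about 0.0325. That is right if 0.03 is the SD of what is analysed. Without a stated drop-out rate, 28 and 16 are margins by subtraction, not planned allowances, and the original SAP's carrying forward of last values would keep some participants in the analysis. This limits the practical weight of the 73% figure but leaves the stated basis for 100 incorrect.

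Finally, the two SDs need not contradict each other. One belongs to a cross-sectional comparison with healthy controls, the other to a treatment effect in a randomised comparison. This is fair, and 0.03 is not shown to be wrong. The low-power figures apply only under their stated assumptions. What remains is that the text presents 0.03 beside the mean level and the SAPs leave the analysed variable open, so the reader cannot confirm the benign reading. A t-test on change would also settle the ambiguity, with nearly the same power as ANCOVA.

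**Conclusion.** The concern holds. As printed, the formula and inputs give 84 participants (86 by t-test), not 72. The documents do not settle whether the result is wrong or an input is misprinted or over-rounded. Taken alone the error is modest: at SD 0.03 the full 100 give 86% power, and the cost is a smaller margin for losses.

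The more consequential gap is the unlabelled SD. With a between-person SD of 0.11 at both visits, an assumption taken from the protocol's baseline figure, 0.03 is right only if baseline and follow-up BMD correlate at about 0.96 and the analysis uses that correlation. Power with 100 participants then runs from under 50% at a correlation of 0.90 to over 90% at 0.97, and is about 13% if baseline is ignored. The correlations are illustrative; the documents give none. The point concerns a secondary outcome in the sub-cohort and does not touch the primary analysis.

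**What to change.** 1. Restate the required number as 84 (86 by t-test), or correct whichever input is misprinted or over-rounded, and restate the margin for losses left within 100.
2. Give the SD to two significant figures with its source, say whether it is an SD of level, of change or a residual SD, and explain how it relates to the 0.11 g/cm² in the control-cohort calculation.
3. In the SAP, specify ANCOVA of follow-up lumbar BMD with baseline lumbar BMD as covariate, naming the follow-up visit, in place of a two-sample test whose variable is not stated. Baseline BMD is already collected.
4. If 0.03 cannot be supported as an SD of change or a residual SD, restate the difference that 100 participants can detect.

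The cost is protocol and SAP wording only, with no extra participants, visits or scans. The stated margin for losses becomes smaller if 84 is confirmed.

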- Alcohol abuse resulting in the need for treatment or hospitalization
- Lack of willingness or desire to participate in the study
- Abuse of euphoric substances
- Pregnancy at the time of inclusion

Patients who meet all inclusion criteria and none of the exclusion criteria will be invited to participate in the study.

Withdrawal

Participants will be asked to cease treatment with the project medicine when an exclusion criteria is met:

- Changed treatment strategy for hyperthyroidism (radioiodine therapy, surgery).
- Hypercalcemia or reduced kidney function
- Onset of diseases or initiation of medication intake as listed under exclusion criteria (except systemic glucocorticoid treatment due to thyroid-associated ophthalmopathy).
- Recurrence of hyperthyroidism after discontinuation of anti-thyroid treatment.

The investigator can stop the treatment for a participant if this is deemed necessary for the participant's safety.

In case of pregnancy, the participant can continue with the project medication. Participants in the intensively studied sub-cohort (n=100) will be excluded from further studies during pregnancy, due to the radiation risk associated with the scans. However, the participants can continue in the main study (n=260).

Population size

Vitamin D and relapse risk in Graves' disease

There are no previous human studies with treatment with vitamin D3 supplements. In a medical record review of 90 medical records from patients with GS treated at Region Hospital Silkeborg or Aarhus University Hospital, it was found that $P-25OHD > 45 \text{ nmol/L}$ was associated with a 60% reduced recurrence risk compared to $P-25OHD < 45 \text{ nmol/L}$ (RR 0.40, 95% CI 0.22–0.71). The study also showed a non-significantly reduced recurrence risk in patients who used vitamin D supplements compared to those who did not take such a supplement (RR 0.71; 95% CI 0.42-1.21). Power calculation: In order to show a difference in relapse risk for intervention with vitamin D compared to placebo of 33% (from 50% to 33%), a total of 260 participants must be included in the study, with 50% randomized to placebo and 50% to supplementation with vitamin D. ($\alpha=0.05$; $\beta=0.20$). Drop-outs will be replaced by the inclusion of new participants: Upon the inclusion of participant no. 260, drop-outs will be counted and replaced by the inclusion of new participant until the end of year 2017 when the Inclusion Period ends.

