Investigator allows direct access to source data/documents (including patient records) during monitoring, auditing and inspection from the Research Ethics Committee for Central Region and the GCP unit for Aarhus University Hospital and its partners. The participants are made aware of this and specific consent is obtained in the form of a power of attorney.

All information obtained will be handled in accordance with the Act on the Processing of Personal Data.

Research biobank

A research biobank will be set up where plasma taken from each subject will be stored at -80 degrees Celsius. The material will be analyzed as described under "biochemistry".

After the end of the experiment, remaining material will be transferred to a biobank, where it will be stored for up to 15 years before being destroyed. Participants will be asked to consent to this. The biobank will be notified to the Danish Data Protection Authority in accordance with applicable legislation.

Medicine accounting

The investigator will keep careful records of who the study medication has been delivered to, incl. date and amount of medicine dispensed. In addition, the amount of returned medication will be recorded. In each participant's CRF, the quantity, batch number, and date of dispensing of study medication are noted.

For each participant, treatment compliance will be calculated as the difference between the number of dispensed and returned doses. Regardless of degree of compliance, participants will be encouraged to continue in the trial. If a participant stops taking the project medicine during the course of the study, the time of cessation of taking the study medicine will be noted together with the reason why the participant has stopped taking the medicine. However, the participants will be asked to continue to come to planned control visits, which will improve the quality of subsequent intention-to-treat analyses.

Risks, side effects and inconvenience

Risks

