Upon inclusion, all test subjects will be informed orally and in writing about any symptoms of hypercalcaemia, and will be asked to contact the investigator immediately. The investigator will, by continuous contact with the test subjects, every 3-6 months, inquire about side effects and possible symptoms of hypercalcaemia. If this is suspected, the subject will be requested to have a blood test carried out as soon as possible to determine serum creatinine and serum ionized calcium. Persistently elevated s-calcium or s-creatinine, which does not decrease on repeated checks, when other possible calcium and vitamin D are discontinued and the patient is biochemically well treated for his Grave's disease, will lead to discontinuation of study medication and exclusion from the study. If the hypercalcemia persists thereafter, the patient will be offered a referral for investigation for hypercalcemia if necessary.

In the toxic phase of Graves' disease, mild hypercalcemia is a frequent and transient phenomenon and in this phase, elevated values will be acceptable if they show a stagnant/declining trend in a repeated control blood test: The subject will be asked to continue the project medication and simply repeat ionized calcium and p-creatinine after another week and as needed.

No biochemical abnormalities are expected as a result of the treatment. Should participants develop symptoms compatible with hypercalcemia (thirst, polyuria, dehydration, confusion), they

will be examined for this in accordance with current clinical guidelines. If hypercalcemia is found to be the cause of the symptoms, the treatment will be discontinued.

Participants are advised not to start supplemental treatment with vitamin D, in addition to the supplement they may receive through the project medication. Participants who, despite this, start taking a supplement of more than 10 micrograms/day will be excluded. Participants will be asked to inform the Investigator if they are put on medical treatment or start taking nutritional supplements or using herbal remedies.

In relation to the subjects' participation in the study, the Investigator will ensure that the participants are informed about and receive/are referred to relevant treatment for diseases/conditions that arise during the study period, including that any side effects to the treatment are handled/treated in the best interest of the trial participant.

Disadvantage

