Some of the participants may find it uncomfortable to have a blood test. There is a minimal risk of infection at the injection site. During blood sampling, a total of around 320 ml of blood will be drawn for participants from the regional hospitals and 470 ml of blood for participants in the intensive examination program and for participants recruited from Aarhus University Hospital, which is not expected to cause discomfort.

The local anesthetic for the fat and muscle biopsy may be associated with pain, and there may be tenderness in the area afterwards. The muscle test will leave a small scar on the thigh and the fat test may cause a bruise. There is a small risk of infection and, in rare cases, a small collection of blood may occur, causing additional soreness for a few days.

For the sub-cohort of 100 subjects, a time consumption of approx. three hours for each of the three study days. The time consumption for the planned forth examination is also approximately three hours.

This examination does not require additional attendance, as the examinations will be able to be done in connection with the participant being in for the planned end-of-study blood test anyway. Completing questionnaires is assumed to take 30 minutes.

Side effects and events

No side effects are expected for the project drug.

At the start of the study, the participants will be informed orally and in writing to contact the Investigator if they experience incidents and side effects, including serious ones during the treatment. At each control visit, the participants will be asked about this. In the specific situation, it will be assessed whether the incident / side effect in question is of such a nature that the participant must withdraw from the study. In each case, this must be explained in the CRF. To ensure that all events / side effects are reported to the relevant authorities, a list will also be kept on which the randomization number and date of registration of the event / side effect are stated, each time such an event is registered. In addition, it is recorded on the list whether the incident / side effect in question has been immediately reported.

Serious incidents and serious side effects related to the treatment will be immediately reported to the Scientific Ethics Committee for Central Denmark Region. All events and side effects will also be reported on a form at the end of the trial.

Time and place

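### Safety measures excludes participants with persistently raised calcium or creatinine from the study, although Withdrawal only stops their medicine and Medicine accounting keeps them in follow-up

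*Combined protocol and SAP*

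**What the plan says.** Several parts of the protocol say what happens when a safety or eligibility problem appears after randomisation.

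- **Withdrawal.** "Participants will be asked to cease treatment with the project medicine when an exclusion criteria is met". The listed triggers include "Hypercalcemia or reduced kidney function". On safety grounds generally, "The investigator can stop the treatment for a participant". Nothing here ends participation in the study.
- **Medicine accounting.** "Regardless of degree of compliance, participants will be encouraged to continue in the trial". Those who stop the medicine are asked to keep coming to planned visits, and the stated reason is the quality of the intention-to-treat analysis.
- **Safety measures, calcium and creatinine.** Values that stay raised on repeat checks, once other calcium and vitamin D have been stopped and the Graves' disease is biochemically well treated, "will lead to discontinuation of study medication and exclusion from the study". A later paragraph of the same section says that symptomatic hypercalcemia leads to stopping treatment, and nothing more.
- **Safety measures, supplements.** "Participants who, despite this, start taking a supplement of more than 10 micrograms/day will be excluded". The sentence does not say from what. The nearest entry criterion reads "Daily intake of vitamin D supplements of more than 10 micrograms, which the participant wishes to continue".
- **Side effects and events.** Each event is assessed for whether it is "of such a nature that the participant must withdraw from the study".
- **Statistical analysis plan, final.** Study withdrawal and exclusion are its examples of an unknown outcome. Such participants enter the ITT analysis as all failures or all successes. The per-protocol analysis keeps only those whose outcome can be assessed.

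**The concern.** A site that finds persistent hypercalcemia has two instructions: stop the tablet and keep the participant in follow-up, or stop the tablet and end participation. The primary outcome runs to about 12 months after anti-thyroid treatment ends, so an early exclusion can come long before it is known.

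The trigger is a post-randomisation event that vitamin D may cause, so the loss cannot be assumed independent of treatment. It need not fall on one arm, however. Safety measures describes mild hypercalcemia as frequent in the toxic phase of the disease itself, creatinine also triggers the rule, and placebo participants can start supplements.

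The loss is avoidable, because stopping a tablet does not require stopping outcome collection.

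**Working it through.** **Comparing the rules**

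| Event | Withdrawal / Medicine accounting | Safety measures |
|---|---|---|
| Hypercalcemia with symptoms | Stop medicine, keep attending | Stop treatment |
| Persistently raised calcium or creatinine | Stop medicine, keep attending | Stop medicine and leave the study |
| Own vitamin D above 10 micrograms/day | Close to an entry criterion; if treated as one, stop medicine | Excluded, object not stated |

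The second row is a direct conflict. Safety measures also differs within itself, since hypercalcemia with symptoms has the milder consequence. The third row is an ambiguity.

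**The plan's sample size.** Inputs from Population size: 50% v 33%, alpha 0.05 (taken as two-sided), power 80%, equal arms. With mean risk 0.415:

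n = [1.96 × √(2 × 0.415 × 0.585) + 0.8416 × √(0.5 × 0.5 + 0.33 × 0.67)]² / 0.17² = 130.7

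That is 131 per arm or 262 in total, in line with the stated 260. Power at 130 per arm is 79.8%.

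**Effect of lost outcomes.** The documents give no exclusion rate, so the numbers lost are assumptions. At the planned risks there are 65/130 failures on placebo and 43/130 on vitamin D, RR 0.66. Chi-square without continuity correction = 260 × (43 × 65 − 65 × 87)² / (130 × 130 × 108 × 152) = 7.67, p = 0.0056.

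With kv and kp outcomes unknown, observed failures are fv = (130 − kv) × 43/130 and fp = (130 − kp) × 0.5, rounded to whole people (62.5 taken as 62). The best case uses fv/130 v fp/130; the worst case uses (fv + kv)/130 v (fp + kp)/130. Each unknown outcome moves its own arm's two cases apart by 1/130 = 0.77 percentage points.

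| Lost: vitamin D, placebo | Best case | Worst case |
|---|---|---|
| 2, 2 | 42 v 64, RR 0.66 | 44 v 66, RR 0.67, p = 0.006 |
| 5, 5 | 41 v 62, RR 0.66 | 46 v 67, RR 0.69, p = 0.009 |
| 4, 0 | 42 v 65, RR 0.65 | 46 v 65, RR 0.71, p = 0.017 |
| 9, 0 | 40 v 65, RR 0.62 | 49 v 65, RR 0.75, p = 0.046 |
| 10, 0 | 40 v 65, RR 0.62 | 50 v 65, RR 0.77, p = 0.061 |
| 0, 4 | 43 v 63, RR 0.68, p = 0.012 | 43 v 67, RR 0.64, p = 0.003 |
| 0, 10 | 43 v 60, RR 0.72, p = 0.031 | 43 v 70, RR 0.61, p = 0.0007 |

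If ten lost vitamin D participants count as drop-outs and are replaced in the same arm, the worst case is (43 + 10)/140 v 65/130, RR 0.76, p = 0.044.

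**Power.** With a fraction x lost in each arm, the worst-case risks are 0.5(1 − x) + x and 0.33(1 − x) + x. Power falls from 79.8% to 77.8% at x = 2% and 74.8% at 5%. If only the vitamin D arm loses outcomes, worst-case power is 72.7% at 2% and 60.4% at 5%.

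**The case against.** Four arguments deserve an answer.

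- **Graded reading.** The calcium and creatinine rule needs persistence after several steps, so it could be a second stage: stop the drug first, and end participation only if the problem does not resolve. But the sentence imposes both consequences together, and Medicine accounting makes no exception for a second stage.
- **Loose terminology.** This is an English translation, and the Withdrawal section is itself about stopping medicine, so exclusion may have been meant in that sense. That is plausible for the supplement sentence. It does not explain a sentence that names stopping the medication and leaving the study as separate consequences.
- **Outcomes can still be obtained or bounded.** Data collection obtains consent to follow the disease course in medical charts, some excluded participants may already have met a failure criterion, and the final SAP keeps the rest in the ITT analysis under two scenarios. This stands as a limit on the harm: loss is possible, not certain. But no text says that chart collection continues after exclusion, and bounding does not recover an outcome.
- **Drop-outs are replaced.** Replacement ends with 2017, while the study is expected to run into 2021, so later exclusions are not covered.

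Two stronger readings are tempting. A reader might infer that side effects also remove people from the study as a rule. Side effects and events provides a case-by-case assessment, and that section also covers harms from blood sampling and biopsies, for which stopping a tablet would be the wrong remedy. A reader might also infer that supplement users are certainly removed from the study; the sentence does not say so.

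**Conclusion.** The conflict over persistently raised calcium or creatinine is real and stands in the current text; the supplement rule is an ambiguity beside it. The severity is minor. Safety measures expects no biochemical abnormalities from treatment, and the rule applies only to persistent values in well-treated disease, so few participants are likely to be affected.

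The practical effect is an avoidable widening of the best-to-worst range. The documents do not support inferring that the trial's conclusion would probably change. At the planned effect, that needs at least ten losses, all on vitamin D, all unreplaced and all counted as failures. This rests on the planned risks, 130 per arm and outcomes that really are not obtained; a smaller true effect would leave less margin.

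**What to change.** 1. **Safety measures, calcium and creatinine.** Replace the consequence with: *discontinuation of study medication; the participant is asked to continue planned visits and outcome collection, including from medical charts*.
2. **Safety measures, supplements.** Replace the exclusion with: *will be asked to stop the project medicine and to continue planned visits and outcome collection*.
3. **Side effects and events.** Keep the investigator's case-by-case judgement to stop the medicine or particular study procedures. Add only that primary outcome collection, at least from charts under the consent described in Data collection, continues unless the participant withdraws consent.

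The Withdrawal section is unchanged, so no drug stop is delayed, and a participant's own right to leave the study is untouched. No visit or measurement is added. The cost is a small protocol amendment with its approval.
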